# 5.2.4 Selected Adverse Events

Additional data will be collected for the following selected adverse events:

- Loss of VA ≥30 letters, compared with the last assessment of VA prior to the most recent assessment, lasting more than 1 hour due to study drug treatment
- CNV conversion requiring treatment for either the study eye or non-study eye
- Any clinically significant ocular imaging finding

# 5.3 METHODS AND TIMING FOR CAPTURING AND ASSESSING SAFETY PARAMETERS

The investigator is responsible for ensuring that all adverse events (see Section 5.2.1 for definition) are recorded on the Adverse Event eCRF and reported to the Sponsor in accordance with instructions provided in this section and in Section 5.4–Section 5.6.

For each adverse event recorded on the Adverse Event eCRF, the investigator will make an assessment of seriousness (see Section 5.2.2 for seriousness criteria), severity (see Section 5.3.3), and causality (see Section 5.3.4).

# 5.3.1 Adverse Event Reporting Period

Investigators will seek information on adverse events at each patient contact. All adverse events, whether reported by the patient or noted by study personnel, will be recorded in the patient's medical record and on the Adverse Event eCRF.

After informed consent has been obtained but prior to initiation of study drug, only serious adverse events caused by a protocol-mandated intervention (e.g., invasive procedures such as biopsies, discontinuation of medications) should be reported (see Section 5.4.2 for instructions for reporting serious adverse events).

After initiation of study drug, all adverse events will be reported until 28 days after the final dose of study drug. After the 28-day period, only serious adverse events (1) caused by a protocol-mandated intervention (e.g., invasive procedures such as aqueous humor sample), or (2) believed to be related to prior study drug treatment (see Section 5.6) should be reported (see Section 5.4.2 for instructions for reporting serious adverse events).

Instructions for reporting adverse events that occur after the adverse event reporting period are provided in Section 5.6.

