#### 5.3.5.10 Deaths

All deaths that occur during the protocol-specified adverse event reporting period (see Section 5.3.1), regardless of relationship to study drug, must be recorded on the Adverse Event eCRF and immediately reported to the Sponsor (see Section 5.4.2).

Death should be considered an outcome and not a distinct event. The event or condition that caused or contributed to the fatal outcome should be recorded as the single medical concept on the Adverse Event eCRF. Generally, only one such event should be reported. If the cause of death is unknown and cannot be ascertained at the time of reporting, "unexplained death" should be recorded on the Adverse Event eCRF. If the cause of death later becomes available (e.g., after autopsy), "unexplained death" should be replaced by the established cause of death. The term "sudden death" should not be used unless combined with the presumed cause of death (e.g., "sudden cardiac death").

Deaths that occur after the adverse event reporting period should be reported as described in Section 5.6.

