### 5.4 IMMEDIATE REPORTING REQUIREMENTS FROM INVESTIGATOR TO SPONSOR

Certain events require immediate reporting to allow the Sponsor to take appropriate measures to address potential new risks in a clinical trial. The investigator must report such events to the Sponsor immediately; under no circumstances should reporting take place more than 24 hours after the investigator learns of the event. The following is a list of events that the investigator must report to the Sponsor within 24 hours after learning of the event, regardless of relationship to study drug:

- Serious adverse events (defined in Section 5.2.2; see Section 5.4.2 for details on reporting requirements)
- Adverse events of special interest (defined in Section 5.2.3; see Section 5.4.2 for details on reporting requirements)
- Pregnancies (see Section 5.4.3 for details on reporting requirements)

For serious adverse events and adverse events of special interest, the investigator must report new significant follow-up information to the Sponsor immediately (i.e., no more than 24 hours after becoming aware of the information). New significant information includes the following:

- New signs or symptoms or a change in the diagnosis
- Significant new diagnostic test results
- Change in causality based on new information
- Change in the event's outcome, including recovery
- Additional narrative information on the clinical course of the event

Investigators must also comply with local requirements for reporting serious adverse events to the local health authority and IRB/EC.

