#### 5.4.2.2 Events That Occur after Study Drug Initiation

After initiation of study drug, serious adverse events, adverse events of special interest, should be reported within 24 hours after learning of the event until the final study visit (Week 76). Investigators should record all case details that can be gathered immediately (i.e., within 24 hours after learning of the event) on the Adverse Event eCRF and submit the report via the EDC system. A report will be generated and sent to Safety Risk Management by the EDC system.

In the event that the EDC system is unavailable, the paper Clinical Trial Serious Adverse Event/Adverse Event of Special Interest Reporting Form provided to investigators should be completed and submitted to the Sponsor or its designee immediately (i.e., no more than 24 hours after learning of the event), either by faxing or by scanning and emailing the form using the fax number or email address provided in Section 5.4.2.1. Once the EDC system is available, all information will need to be entered and submitted via the EDC system.

Instructions for reporting serious adverse events that occur after the final study visit (Week 76) are provided in Section 5.6.

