### 5.6 ADVERSE EVENTS THAT OCCUR AFTER THE ADVERSE EVENT REPORTING PERIOD

The Sponsor should be notified if the investigator becomes aware of any serious adverse event that occurs after the end of the adverse event reporting period (defined as 28 days after the final dose of study drug), if the event is believed to be related to prior study drug treatment or to a protocol-mandated intervention (see Section 5.3.1). These events should be reported through use of the Adverse Event eCRF. However, if the EDC system is not available, the investigator should report these events directly to the Sponsor or its designee, either by faxing or by scanning and emailing the Clinical Trial Serious Adverse Event/Adverse Event of Special Interest Reporting Form using the fax number or email address provided below:

Email address: us\[contact]

[contact]

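### Before Week 76 the protocol has two unreconciled end points for reporting SAEs and deaths that the site judges neither drug-related nor procedure-caused

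*Combined protocol and SAP*

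**What the plan says.** **The 28-day rule.** Section 5.3.1 asks for all adverse events up to 28 days after the last dose. It then restricts reporting: "After the 28-day period, only serious adverse events (1) caused by a protocol-mandated intervention", or SAEs believed related to prior study drug. Footnote aa of both schedules of activities has the same restriction. Section 5.6 takes over at the "end of the adverse event reporting period (defined as 28 days after the final dose of study drug". On deaths, Section 5.3.5.10 requires immediate reporting regardless of relationship for "All deaths that occur during the protocol-specified adverse event reporting period", and adds: "Deaths that occur after the adverse event reporting period should be reported as described in Section 5.6".

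**The Week 76 rule.** Section 5.4 requires SAEs and AESIs "within 24 hours after learning of the event, regardless of relationship to study drug". Section 5.4.2.2 says that, once study drug has started, these events "should be reported within 24 hours after learning of the event until the final study visit (Week 76". It then hands over: "Instructions for reporting serious adverse events that occur after the final study visit (Week 76) are provided in Section 5.6".

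**How the sections are linked.** Section 5.3 says events are to be recorded and "reported to the Sponsor in accordance with instructions provided in this section and in Section 5.4–Section 5.6", so it invokes both rules together. Section 5.3.1 and footnote aa state the 28-day rule and then send the reader to Section 5.4.2 for SAE instructions, where the Week 76 rule stands.

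**The concern.** The two rules cannot both be followed. Take an SAE or death at Week 74 in a patient who completed dosing, judged by the site to be neither drug-related nor procedure-caused. Sections 5.4 and 5.4.2.2 require it within 24 hours. Sections 5.3.1 and 5.6 and footnote aa do not ask for it. Section 5.6 has two different starting points, its own and the one that Section 5.4.2.2 gives it.

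At stake is how completely serious events reach the Sponsor late in follow-up and after early treatment stop. Under the 28-day rule, the site's causality judgement decides what is sent. Section 5.7 lets the Sponsor upgrade that judgement, and Section 5.1.1.2 relies on a masked aggregate review and on an unmasked IMC review for imbalances between arms. These safeguards work only on events that have been received. SAEs judged unrelated do occur: Section 1.3.2 reports two Phase I participants with systemic SAEs, none assessed as related.

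**Working it through.** **Inputs.** Last scheduled dose at Week 68 (Q4W) or Week 64 (Q8W), final visit at Week 76, and 18 or 9 treatments (Section 3.1). Visit windows of ±5 days (Appendices 1 and 2). Planned patients on Q4W schedules: 144 drug + 72 sham = 216. On Q8W schedules: 72 drug + 72 sham = 144.

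**1. The plan's own dose counts.** Q4W: 68/4 + 1 = 18. Q8W: 64/8 + 1 = 9. Both match, which confirms the last-dose weeks.

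**2. Length of the conflict for patients who complete dosing.** The 28-day rule ends full reporting at last-dose week + 4.

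- Q4W: 68 + 4 = Week 72. Gap to Week 76 = 4 weeks (28 days).
- Q8W: 64 + 4 = Week 68. Gap to Week 76 = 8 weeks (56 days).
- With ±5 days at both the last-dose visit and the final visit, the gap moves by up to 10 days: 18–38 days (Q4W) and 46–66 days (Q8W). It is never zero.

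**3. Planned person-time in conflict, if all patients complete.** 216 × 4 + 144 × 8 = 864 + 1,152 = 2,016 person-weeks. Total: 360 × 76 = 27,360. Share: 2,016/27,360 = 7.4%.

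**4. Patients who stop treatment but stay.** For a last dose at week *w*, the gap is 76 − (*w* + 4): 60, 48 and 24 weeks for *w* = 12, 24 and 48. Section 4.6.1 strongly encourages such patients to remain in the study.

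**5. Which events are affected between the 28-day cut-off and Week 76.**

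| Event | 5.3.1, 5.6, footnote aa | 5.4, 5.4.2.2 |
|---|---|---|
| SAE believed drug-related | report | report |
| SAE caused by a study procedure | report | report |
| SAE or death judged neither | not asked for | report within 24 hours |
| Non-serious AESI | not asked for | report within 24 hours |
| Other non-serious event | not asked for | not covered |

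Section 5.4.2.2 does not name deaths. They fall under it as fatal SAEs (Section 5.2.2), so that row holds for deaths by inference. The AESI row is nearly empty: sight-threatening AESIs must be reported as SAEs (Section 5.2.3), and contamination and medication errors arise from the study drug or its administration. What remains is mainly a Hy's Law case reported only as an AESI (Section 5.3.5.9).

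**6. Illustrative event count.** The documents give no 76-week SAE rate. Assume a constant hazard λ = −ln(1 − *p*)/76, where *p* is the 76-week incidence, and 85% completing (from the 15% dropout assumption in Section 6.1, which concerns study dropout, not completion of dosing). Expected patients whose first SAE falls in the gap:

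0.85 × [216(e^(−72λ) − e^(−76λ)) + 144(e^(−68λ) − e^(−76λ))]

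This gives 1.7 at *p* = 8%, 4.1 at 20% and 5.7 at 30%. The first two rates equal the Phase I fractions (2 of 25 overall, 2 of 10 in the multiple-dose stage), for which no follow-up length is given. The 30% is an assumption without a source. Among patients who complete, each figure is an upper bound, because it treats every such SAE as judged unrelated.

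**The case against.** The strongest reply is that little need be lost in practice. Section 5.3.1 opens by having investigators ask about adverse events at every contact and enter all of them on the Adverse Event eCRF, which is also the route by which Section 5.4.2.2 sends reports to the Sponsor. Both schedules mark adverse-event collection at Weeks 72 and 76. Table 3 treats an event as related unless evidence points elsewhere, and related SAEs are reportable under both rules. A site that follows the cross-reference from Section 5.3.1 to Section 5.4.2 arrives at the Week 76 rule.

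Much of this stands. A reader might infer that unrelated late SAEs and deaths will go unreported. The documents do not support that: non-capture is possible, not certain. But the restricting sentence in Section 5.3.1 conflicts with that section's own opening, and it permits a site not to report. The cross-reference does not rank the rules either, because Section 5.6 keeps its own 28-day start. Nor can Section 5.4.2.2 be read as setting only the 24-hour clock, since it states its own end point and its own hand-over.

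Three further inferences should not be drawn. Drug and sham on the same schedule have the same window, so no between-arm bias is shown. Nothing here touches the primary or secondary efficacy endpoints. The 28-day window for non-serious events is consistently stated and is not challenged.

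**Conclusion.** The contradiction is real and stands in current operative text. For SAEs and deaths judged neither drug-related nor procedure-caused, whether a report is required before Week 76 depends on which section the site follows. The conflict lasts a nominal 4 weeks (Q4W) or 8 weeks (Q8W) in patients who complete dosing, 7.4% of planned person-time if all complete, and 24 weeks after a last dose at Week 48 in a patient who stays. These lengths follow from the protocol's calendar alone. The event counts are illustrative only, because they rest on assumed rates. The case for correction rests on the kind of event affected and the low cost of repair, not on a demonstrated loss of data. It should be fixed.

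**What to change.** Reconcile Sections 4.6.2, 5.3.1, 5.3.5.10, 5.4.2.2 and 5.6 and footnote aa of both schedules to one end point for SAEs, deaths and AESIs regardless of causality. Set it no earlier than the Week 76 visit already in Section 5.4.2.2, and start Section 5.6 at that same point.

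For patients who leave the study early without withdrawing consent, keep the follow-up of SAEs, deaths and AESIs that Section 4.6.2 already asks for. Ending at the early-termination visit could lose events that the present text would keep.

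An amendment date separates before from after, but it does not show which rule a site had been following. So query sites once for SAEs and deaths after the 28-day cut-off that were not reported.

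The cost is one amendment with IRB/EC approval, the one-time query and a few more SAE entries. No visit or assessment is added.

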# 5.3.2 Eliciting Adverse Event Information

A consistent methodology of non-directive questioning should be adopted for eliciting adverse event information at all patient evaluation timepoints. Examples of non-directive questions include the following:

"How have you felt since your last clinic visit?"

"Have you had any new or changed health problems since you were last here?"

# 5.3.3 Assessment of Severity of Adverse Events

The WHO toxicity grading scale (see Appendix 15) will be used for assessing adverse event severity. Table 2 will be used for assessing severity for adverse events that are not specifically listed in the WHO toxicity grading scale.

For adverse events of IOI, severity assessment ideally should be aligned with the grading scale for assessment of anterior chamber flare or cells and vitreous chamber (see Appendix 6).

Table 2 Adverse Event Severity Grading Scale for Events Not Specifically Listed in WHO Toxicity Grading Scale

Grade	Severity
1	Mild; transient or mild discomfort (<48 hours); no medical intervention or therapy required
2	Moderate; mild to moderate limitation in activity; some assistance may be needed; no or minimal medical intervention or therapy required
3	Severe; marked limitation in activity; some assistance usually required; medical intervention or therapy required; hospitalization possible
4	Life-threatening; extreme limitation in activity; significant assistance required; significant medical intervention or therapy required, hospitalization or hospice care probable

Notes: Developed by the Division of Microbiology and Infectious Diseases.

Regardless of severity, some events may also meet seriousness criteria. Refer to definition of a serious adverse event (see Section 5.2.2).

## 5.3.4 Assessment of Causality of Adverse Events

Investigators should use their knowledge of the patient, the circumstances surrounding the event, and an evaluation of any potential alternative causes to determine whether an adverse event is considered to be related to the study drug, indicating "yes" or "no" accordingly. The following guidance should be taken into consideration (see also Table 3):

- Temporal relationship of event onset to the initiation of study drug
- Course of the event, with special consideration of the effects of dose reduction, discontinuation of study drug, or reintroduction of study drug (as applicable)
- Known association of the event with the study drug or with similar treatments
- Known association of the event with the disease under study
- Presence of risk factors in the patient or use of concomitant medications known to increase the occurrence of the event
- Presence of non-treatment-related factors that are known to be associated with the occurrence of the event

#### Table 3 Causal Attribution Guidance

Is the adverse event suspected to be caused by the study drug on the basis of facts, evidence, science-based rationales, and clinical judgment?

YES There is a plausible temporal relationship between the onset of the adverse event and administration of the study drug, and the adverse event cannot be readily explained by the patient's clinical state, intercurrent illness, or concomitant therapies; and/or the adverse event follows a known pattern of response to the study drug; and/or the adverse event abates or resolves upon discontinuation of the study drug or dose reduction and, if applicable, reappears upon re-challenge.

NO An adverse event will be considered related, unless it fulfills the criteria specified below. Evidence exists that the adverse event has an etiology other than the study drug (e.g., preexisting medical condition, underlying disease, intercurrent illness, or concomitant medication); and/or the adverse event has no plausible temporal relationship to administration of the study drug (e.g., cancer diagnosed 2 days after first dose of study drug).

# 5.3.5 Procedures for Recording Adverse Events

Investigators should use correct medical terminology/concepts when recording adverse events on the Adverse Event eCRF. Avoid colloquialisms and abbreviations.

Only one adverse event term should be recorded in the event field on the Adverse Event eCRF.

### 5.3.5.1 Adverse Events of Ocular Infection and Inflammation

For the purposes of reporting events of ocular infection and inflammation, the following terms and definitions should be used:

- Iritis: the presence of inflammatory cells in the anterior chamber
  - The presence of aqueous flare alone will not constitute iritis but should be documented as an anterior chamber flare for adverse event reporting purposes.
- Iridocyclitis: the presence of inflammatory cells in both the aqueous and vitreous
- Vitritis: the presence of active inflammation in the vitreous, demonstrated by the presence of inflammatory cells (trace or greater)
  - Active inflammation in the vitreous should be clinically differentiated from cellular debris from prior episodes of inflammation, hemorrhage, or other causes.
- IOI-associated retinal vasculitis: ocular inflammation and retinal vascular changes (i.e., perivascular sheathing and vascular leakage or occlusion on fluorescein angiogram), as defined by the Standardization of Uveitis Nomenclature Working Group (Jabs et al. 2005).
  - The presence of occlusive retinal vasculopathy, in the absence of visible inflammation, should not be considered IOI-associated retinal vasculitis.
- Endophthalmitis: diffuse intraocular inflammation predominantly involving the vitreous cavity but also involving the anterior chamber, implying a suspected underlying infectious cause.
  - A culture is required prior to initiating antibiotic treatment for presumed endophthalmitis. Results of bacterial or fungal cultures, treatment given, and final ophthalmologic outcome must be provided in the details section of the Adverse Event eCRF.

Note: Trace benign, aqueous pigmented cells visible on slit lamp examination that are caused by the dilation process and are not red blood cells, white blood cells, or the result of any ocular disorder should not be recorded as an adverse event.

### 5.3.5.2 Increased Intraocular Pressure Values

The observation of elevated IOP values measured between 30–50 minutes post-injection, in general, should not be reported as an adverse event. Elevated IOP values measured between 30–50 minutes post-injection should be reassessed at 60–80 minutes post-injection prior to reporting an adverse event. Medical and scientific judgment should be exercised in deciding if an elevated IOP at 30–50 minutes post-injection that remains elevated at the follow-up 60–80 minute assessment is clinically significant and qualifies to be reported as an adverse event.

# 5.3.5.3 Abnormal Findings on Ocular Imaging

Not every abnormal imaging finding on ocular imaging qualifies as an adverse event. An abnormal finding on ocular imaging must be reported as an adverse event if it meets any of the following criteria:

- Is accompanied by clinical symptoms
- Results in a change in study treatment (e.g., dosage modification, treatment interruption, or treatment discontinuation)
- Results in a medical intervention or a change in concomitant therapy
- Is clinically significant in the investigator's judgment

It is the investigator's responsibility to review all ocular images. Medical and scientific judgment should be exercised in deciding whether an isolated imaging abnormality should be classified as an adverse event.

If a clinically significant abnormal image finding is a sign of a disease or syndrome (e.g., retinal edema), only the diagnosis (i.e., CNV) should be recorded on the Adverse Event eCRF.

Observations of the same clinically significant abnormal image finding from visit to visit should only be recorded once on the Adverse Event eCRF (see Section 5.3.5.6 for details on recording persistent adverse events).

# 5.3.5.4 Diagnosis versus Signs and Symptoms

A diagnosis (if known) should be recorded on the Adverse Event eCRF rather than individual signs and symptoms (e.g., record only liver failure or hepatitis rather than jaundice, asterixis, and elevated transaminases). However, if a constellation of signs and/or symptoms cannot be medically characterized as a single diagnosis or syndrome at the time of reporting, each individual event should be recorded on the Adverse Event eCRF. If a diagnosis is subsequently established, all previously reported adverse events based on signs and symptoms should be nullified and replaced by one adverse event

report based on the single diagnosis, with a starting date that corresponds to the starting date of the first symptom of the eventual diagnosis.

